15.6 Multiplicity

Overall type I error will be maintained at 5% level using the sequential testing approach summarized in the figure below.

15.7 Safety Analysis

15.7.1 Primary Safety

Co-primary safety endpoints are adverse events and monocular mesopic contrast sensitivity (with and without glare).

15.7.1.1 Adverse Events

Descriptive summaries (counts and percentages) for specific AEs including SSIs will be presented by IOL group. The one-sided exact 95% lower confidence limit of incidence rates (proportion of eyes with events) observed for each IOL group will be compared to the cumulative and persistent adverse event SPE rates. In addition to SPE rates predefined in IS EN ISO 11979-7, the rate of adverse events that may be specifically related to ACRYSOF IQ EDF IOL design features; and any other significant events will be provided. These rates will be accompanied by two-sided exact 95% confidence intervals.

The number and percentage of all adverse events will be tabulated with a breakdown by IOL group and implanted eye. A listing of all adverse events will also be provided.

The number and percentage of secondary surgical interventions (SSIs) that may be related to optical characteristics of the lens will be tabulated with a breakdown by IOL group and implanted eye.

15.7.1.2 Mesopic contrast sensitivity (with and without glare)

All measured contrast sensitivity values will be converted to logarithmic form before performing statistical calculations. Analyses of log contrast sensitivity will be performed for each testing condition and spatial frequency. If a subject is unable to see a targeted spatial frequency at any available contrast (including the contrast of the reference patch), the lowest contrast score will be given, preceded by the appropriate inequality symbol (<) to indicate that the actual sensitivity is below the given value. Prior to any averaging or other statistical calculations, all contrast threshold values will be converted to log contrast sensitivity values. The number and percentage of subjects who cannot see any contrast will be recorded and tabulated for each spatial frequency to provide a qualitative extent of the bias. Descriptive statistics will include number of eyes, mean, standard deviation, median, minimum, maximum, and additional percentiles (10th, 25th, 75th, and 90th percentiles). Descriptive tables will include a note that the corresponding mean values are biased upward and variability values are biased downward (using < and > symbols). The 5th percentile of log contrast sensitivity values will be calculated for the control group, then the percentage of eyes in the test group that achieved a log contrast sensitivity lower than this value will be presented.

In addition, for mesopic contrast sensitivity, descriptive summary statistics will be presented by IOL group and 3 mesopic pupil size ranges: <3.0 mm (small), ≥ 3.0 mm to ≤ 4.0 mm (medium), and >4.0 mm (large).

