8.3 Co-Primary Safety Objective

Below are listed the study's co-primary safety objectives. Each objective is assessed at Visit 4A (120-180d postoperative).

1. The study's primary safety objective is to demonstrate that ACRYSOF IQ EDF IOL adverse event rates are not worse than the historical control SPE rates, as defined in IS EN ISO 11979-7:2014
2. To describe monocular mesopic contrast sensitivity test (with and without glare) outcomes

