9.3 Rationale for Choice of Control Article

ACRYSOF IQ EDF IOL is a modification of the United States (US) Food and Drug Administration (FDA) approved, commercially available control article (ACRYSOF IQ Monofocal IOL). The control article has the same physical properties and is composed of the same material as the test article. Based on optical bench testing and simulation of the test article, the contrast sensitivity under mesopic conditions is expected to be comparable to the

control article. Further, the ACRYSOF IQ Monofocal IOL is well established in the literature and is considered the industry standard of care. For these reasons, the ACRYSOF IQ Monofocal IOL is scientifically the most appropriate control article for this study, and functions to reduce bias.

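### The protocol's only stated between-lens statistic for mesopic contrast sensitivity, the percentage of test eyes below the control sample's 5th percentile, has no interval, ignores the cut-off's sampling error, and separates losses up to about 0.5 SD poorly from no difference

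*Protocol*

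**What the plan says.** Section 15.7.1 gives the endpoint its rank: "Co-primary safety endpoints are adverse events and monocular mesopic contrast sensitivity (with and without glare"). Section 8.3 limits the aim: "To describe monocular mesopic contrast sensitivity test (with and without glare) outcomes". No hypothesis, margin or success rule is attached.

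Section 15.7.1.2, repeated almost in full in the synopsis, sets the analysis for each testing condition and spatial frequency:

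- Summaries: "Descriptive statistics will include number of eyes, mean, standard deviation, median, minimum, maximum, and additional percentiles (10th, 25th, 75th, and 90th percentiles").
- Floor scores: an eye that sees no available contrast receives the lowest score with an inequality sign. The number of such subjects is tabulated, and the tables carry a note that "the corresponding mean values are biased upward and variability values are biased downward".
- Comparison of lenses: "The 5th percentile of log contrast sensitivity values will be calculated for the control group, then the percentage of eyes in the test group" strictly below that value is presented.
- Section 15.7.1.2 only: "descriptive summary statistics will be presented by IOL group and 3 mesopic pupil size ranges".

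Neither place gives the share below the cut-off an interval, and neither plans a difference in means. Elsewhere the protocol does plan a between-lens difference with a 95% CI: for visual acuity (15.4.1.2 and 15.4.2.2) and, among supportive safety items, for posterior capsular opacification and posterior capsulotomy (15.7.3).

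**The concern.** A 5th percentile estimated from 100 eyes lies between about the 5th and 6th lowest values, so it moves a good deal from sample to sample. Counting test eyes below it adds a second layer of sampling error. A figure such as 10%, printed without an interval, could come from two identical lenses or from a moderate loss, and the reader is not told how wide that uncertainty is.

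Floor scores add a second problem. Eyes at floor all share the lowest score, and the rule counts only test eyes strictly lower than the cut-off. If the control 5th percentile falls on the floor score, the statistic is 0% whatever the test lens does.

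At stake is how well a co-primary safety endpoint is described. Some supportive safety items get a more informative comparison.

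**Working it through.** **Inputs.** 100 completers per arm (section 10), one eye per subject. The protocol gives no SD, margin or floor rate for contrast sensitivity, so losses are in SD units and values are taken as normal. Floor effects are left out of steps 1 to 4.

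**Check on N.** The protocol states 84% power for BCDVA with a margin of 0.10, a difference of 0.04 and an SD of 0.16 at one-sided 5%. (0.10 − 0.04) / (0.16 × √(2/100)) = 0.06 / 0.0226 = 2.65; 2.65 − 1.645 = 1.01; Φ(1.01) = 84%. The stated figure reproduces with 100 per arm.

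**1. Identical lenses, exact.** With the cut-off at the k-th lowest of 100 control eyes, the number of 100 test eyes below it is beta-binomial(100, k, 101 − k).

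- k = 5: mean 4.95, SD 3.0, 95% range 0 to 12, P(10 or more) = 8.2%.
- k = 6: mean 5.9, 95% range 1 to 14, P(10 or more) = 14.1%.

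Which k applies depends on the percentile definition. Were the cut-off truly fixed at the population 5th percentile, binomial(100, 0.05) would give 1 to 10.

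**2. Error in the cut-off.** Taken as the average of the 5th and 6th lowest of 100 values, the control cut-off lies between about the 2nd and 10th population percentiles in 95% of samples.

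**3. True losses.** 100,000 simulated trials per row, interpolated 5th percentile. The bound of 13% is the upper end of the null range under that definition and is used here only as a yardstick. The last column is the power of a two-sided 5% t-test of the mean difference, from the noncentral t.

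| True loss | Mean % below cut-off | 95% range | Above 13% | Mean-difference 95% CI excludes 0 |
|---|---|---|---|---|
| 0 | 5.9 | 1–13 | 2.4% | 5% |
| 0.25 SD | 9.3 | 2–19 | 17% | 42% |
| 0.5 SD | 14.1 | 5–26 | 51% | 94% |
| 0.75 SD | 20.4 | 8–35 | 84% | over 99.9% |
| 1.0 SD | 28.0 | 13–44 | 97% | over 99.9% |

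A loss of 0.3 SD averages 8.7% (k = 5) or 10.3% (k = 6), inside the null range, and shows 5% or less in about 24% or 15% of trials.

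**4. Precision of a mean difference.** Half-width = t(0.975, 198) × SD × √(2/100) = 1.972 × 0.1414 × SD = 0.28 SD. For assumed SDs of 0.15, 0.20 and 0.30 log units this is 0.042, 0.056 and 0.084.

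**5. Floor ties (floor rates assumed).** The control 5th percentile equals the floor score once about six of 100 control eyes are at floor. P(6 or more of 100) from the binomial is 38% at a true floor rate of 5% and 94% at 10%. The statistic is then exactly 0%. At a 10% control floor rate, simulation gives 0% in 94% of trials both with no loss and with a true loss of 1 SD.

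**6. Floor scores and the means.** Substituting the floor score raises a mean by SD × [φ(z) + zΦ(z)], where Φ(z) is the share at floor. For control v test shares of 5% v 15%, 20% v 35% and 30% v 50%, the implied true differences are 0.61, 0.46 and 0.52 SD. They shrink by 9%, 27% and 40%, leaving 0.55, 0.33 and 0.32 SD.

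**The case against.** A reader might infer that a real contrast loss cannot be told from noise under this plan. The documents do not support that. The number of eyes, mean and SD are planned, with summaries by lens, so a reader can form a mean difference and a rough 95% CI. A median does not move while fewer than half the eyes are at floor, and floor counts are tabulated. A loss near 1 SD would usually show even in the percentile statistic if few eyes are at floor.

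Nor does floor substitution simply hide a loss. In all three cases of step 6 the shrunken difference still exceeds the half-width of 0.28 SD, and the protocol discloses the bias.

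A reader might also take section 9.3, where "the contrast sensitivity under mesopic conditions is expected to be comparable to the" control article, as the trial question. It is an expectation from bench testing and simulation, given to justify the choice of control. The objective is to describe, so no test or decision rule is invalidated. The proposed mean difference has its own limits: its power at a 0.3 SD loss is only about 56%.

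Finally, it can be said that intervals and extra columns belong in the SAP, which is not shown and may add them. That would settle the matter if the protocol were silent. It is not: it specifies this comparison in detail in two places, and it states differences with intervals for other endpoints. These points narrow the claim but do not answer the lack of any stated precision for the one comparison that the protocol makes.

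**Conclusion.** The point holds in limited form. The protocol's one stated lens-versus-lens statistic for this co-primary safety endpoint has no interval and ignores the sampling error of its cut-off. With 100 eyes per arm and identical lenses it ranges over about 0% to 14%, depending on the percentile definition. It therefore separates losses up to about 0.5 SD poorly from no difference: 51% above the null bound at 0.5 SD, against 94% for a mean-difference CI.

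These figures assume normal values, one eye per subject and no floor effect. The floor-tie failure is conditional on more than about 5% of control eyes scoring at floor, which the protocol neither states nor rules out. No success criterion is affected. The weakness lies in how informative the planned comparison is, and it should be corrected because correction costs almost nothing.

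**What to change.** In section 15.7.1.2 and the synopsis:

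1. For each condition and spatial frequency, in first eyes, add the test minus control mean log contrast sensitivity with a two-sided 95% CI.
2. Keep the percentage below the control 5th percentile, and give it a 95% bootstrap interval that resamples both arms.
3. Because floor scores bias the means upward, add a sensitivity analysis that treats scores marked with the inequality sign as left-censored, wherever floor scores are not rare.

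The cost is some added wording and a few table columns, with no new data, visits or subjects. The censored model brings a normality assumption, confined to the sensitivity analysis. The existing summaries stay as they are.

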15.7.2 Secondary Safety

Secondary safety endpoint is:

- Rates of severe and most bothersome (separately) visual disturbances as reported by the subjects using the QUVID questionnaire

For the secondary safety endpoint, descriptive summaries (counts and percentages) for the severe and most bothersome (separately) visual disturbances as reported by the subjects using the QUVID questionnaire will be presented by IOL group. These rates will be accompanied by two-sided exact 95% confidence intervals.

If QUVID questionnaire generates scores, the cumulative distribution curves showing the percentage of subjects with a given change in their score compared to baseline by IOL group will be presented to help determine whether any observed differences are meaningful.

Counts and percentages of subjects who did not have a given visual disturbance at baseline but developed and present at Visit 4A (120-180d postoperative) will be presented.

In addition, the presence and absence of these symptoms, and how frequent, severe, and bothersome they appear will be summarized by visit with counts and percentages.

15.7.3 Supportive Safety

Intraocular pressure

Descriptive statistics (mean, median, SD, number of eyes, minimum, and maximum) will be presented for IOP by IOL group and implanted eye. A listing of all eyes with an increase or decrease in IOP of more than 10 mmHg at any visit compared to the same eye at baseline will also be provided.

Slit-lamp examination

The number and percentage of all slit lamp examination findings will be tabulated by IOL group and implanted eye. A listing of abnormal slit lamp examination findings will also be provided.

Dilated fundus exam

The number and percentage of all dilated fundus examination findings will be tabulated by IOL group and implanted eye. A listing of abnormal dilated fundus examination findings will also be provided.

IOL observations

The number and percentage of all IOL observations will be tabulated by IOL group and implanted eye.

IOL tilt/decentration

The number and percentage of all eyes with IOL tilt/decentration will be tabulated by IOL group and implanted eye. A listing of all IOL tilt/decentration assessments will also be provided.

Subjective posterior capsular opacification

The number and percentage of eyes within each category of subjective posterior capsule opacification will be tabulated by IOL group and implanted eye. A frequency table of the “worst case” posterior capsule opacification (including capsulotomy) will be presented by IOL group and implanted eye. In addition, the difference in the rate (ACRYSOF IQ EDF IOL minus ACRYSOF IQ Monofocal IOL) and the associated two-sided 95% confidence interval will be presented. A listing of eyes with clinically significant posterior capsule opacification, clinically significant posterior capsule opacification requiring YAG or posterior capsulotomy will be presented.

Posterior capsulotomy

The number and percentage of eyes with PC will be tabulated by IOL group and implanted eye. In addition, the difference in the rate (ACRYSOF IQ EDF IOL minus ACRYSOF IQ Monofocal IOL) and the associated two-sided 95% confidence interval will be presented.

Surgical problems

The number and percentage of all surgical problems will be tabulated by IOL group and implanted eye. A listing of all surgical problems will also be provided.

Other procedures at surgery

A listing of all other procedures at surgery will be provided.

Device Deficiencies

The number and percentage of all device deficiencies will be tabulated with a breakdown by IOL group and implanted eye. A listing of all device deficiencies will also be provided.

15.8 Interim Analyses

Not Applicable.

15.9 Adaptive Study Design

Not Applicable.

The figure consists of a 10x10 grid of black bars. The bars are arranged in 10 rows and 10 columns. The bars in each row are of different lengths, creating a stepped effect. The bars in each column are of equal length. The bars are black on a white background.

16 Ethics

This clinical study must be conducted in accordance with the ethical principles contained within:

- The Declaration of Helsinki (DoH), and in compliance with the International Conference on Harmonization (ICH) E6 GCP Consolidated Guideline
- ISO 14155:2011 Clinical investigation of medical devices for human subjects – Good clinical practice
- SOPs of the Study Sponsor and contract research organizations participating in the conduct of the clinical study and all other applicable regulations.

The Investigator and all clinical study staff must conduct the clinical study in compliance with the protocol. The Investigator must ensure that all personnel involved in the conduct of the study are qualified to perform their assigned responsibilities through relevant education, training, and experience.

Before clinical study initiation, this protocol, the ICF, any other written information given to subjects, and any advertisements planned for subject recruitment must be approved by an IEC/IRB. The Investigator must provide documentation of the IEC/IRB approval to the Study Sponsor. The approval must be dated and must identify the applicable protocol, amendments (if any), ICF, all applicable recruiting materials, written information for subject, and subject compensation programs. The IEC/IRB must be provided with a copy of the any periodic safety updates, and all other information as required by local regulation and/or the IEC/IRB. At the end of the study, the Investigator must notify the IEC/IRB about the study's completion. The IEC/IRB also must be notified if the study is terminated prematurely. Finally, the Investigator must report to the IEC/IRB on the progress of the study at intervals stipulated by the IEC/IRB.

Voluntary informed consent must be obtained from every subject prior to the initiation of any screening or other study-related procedures. The Investigator must have a defined process for obtaining consent. Specifically, the Investigator, or delegate, must explain the clinical study to each potential subject and the subject must indicate voluntary consent by signing and dating the approved ICF. The subject must be provided an opportunity to ask questions of the Investigator, and if required by local regulation, other qualified personnel. The Investigator must provide the subject with a copy of the consent form written in a language the subject understands. The consent document must meet all applicable local laws and provide subjects with information regarding the purpose, procedures, requirements, and restrictions of the

study, along with any known risks and potential benefits associated with the IP, the available compensation, and the established provisions for maintaining confidentiality of personal, protected health information. Subjects will be told about the voluntary nature of participation in the study and must be provided with contact information for the appropriate individuals should questions or concerns arise during the study. The subject also must be told that their records may be accessed by appropriate authorities and Sponsor-designated personnel. The Investigator must keep the original, signed copy of the consent and must provide a duplicate copy to each subject according to local regulations.

The Study Sponsor assures that the key design elements of this protocol will be registered in www.clinicaltrials.gov as required by current regulations and, if applicable, other public databases as required by local country regulations. In addition, results of this study will be made publicly available in www.clinicaltrials.gov regardless of outcome as required by current regulations and, if applicable, in other public databases as required by local country regulations.

Amendments may necessitate that the informed consent and other study-related material be revised. If the consent form is revised, all subjects currently enrolled in the study must sign the approved, revised informed consent, as required by the IEC/IRB.

18 APPENDICES

18.1 Adverse Event Tables

Below are the tables referred to in Section 13 DEVICE DEFICIENCIES AND ADVERSE EVENTS.

Table 18-1 Additional Supportive Characterizations of Ocular Adverse Events

Adverse Event	Definition
Anterior uveitis	Anterior segment inflammation characterized by grade 1+ cell or greater using SUN criteria that is persistent for greater than 3 months after surgery, or relapses in less than 3 months after discontinuation of therapy, or the subject is maintained on therapy for more than 3 months to control inflammation. (Note that any iritis present at the final visit is considered significant and should be counted as a “persistent” ISO SPE event.).
Clinically significant cystoid macular edema	Macular edema diagnosed by clinical examination and adjunct testing (e.g., OCT, FA) resulting in BCDVA of $\leq 20/40$ at ≥ 1 month
Visually significant corneal edema	Corneal swelling (stromal or epithelial) resulting in CDVA of 20/40 or worse at Form 3 (Visit 3A) or later. (Note that any corneal stromal edema present at the final visit is considered significant and should be counted as a “persistent” ISO SPE event.).
Endophthalmitis	Intraocular inflammation requiring diagnostic vitreous tap and intraocular antibiotics
Mechanical pupillary block	Shallowing of anterior chamber due to obstruction of aqueous humor flow from the posterior to anterior chamber through the pupil by the crystalline lens, vitreous face, or implanted device
Increased IOP	Elevation of IOP by ≥ 10 mmHg above baseline to a minimum of 25 mmHg. (Note that any “raised IOP requiring treatment” present at the final visit is considered significant and should be counted as a “persistent” ISO SPE event.).
Rhegmatogenous RD	Partial or complete RD associated with retinal tear
Toxic anterior segment syndrome	Acute, noninfectious inflammation of the anterior segment that starts within 24 to 48 hrs after surgery, usually resulting in hypopyon and commonly presenting with corneal edema, that improves with steroid treatment
Secondary IOL intervention	
Exchange	The investigational device is replaced with the same lens model
Removal	The investigational device is removed and replaced with a non-investigational lens or no lens is implanted
Reposition	The existing IOL is surgically moved to another location or rotated

CDVA = corrected distance visual acuity; FA = fluorescein angiography; IOL = intraocular lens; IOP = intraocular pressure; OCT = optical coherence tomography; RD = retinal detachment; SUN = Standardization of Uveitis Nomenclature

Table 18-2**Definitions of Indications for Device Exchange, Removal, or Reposition**

Indication	Definition
Capsular block syndrome	Hyper-distention of the lens capsular bag due to the IOL optic blocking egress of fluid through the anterior capsulotomy typically inducing a myopic refractive error
Cataract	Any opacification of the crystalline lens with or without reduced visual acuity
Chronic anterior uveitis	Persistent anterior segment inflammation characterized by grade $\geq 1+$ cell using SUN criteria
Endothelial cell loss	Chronic endothelial cell loss at a rate greater than that due to normal aging
Incorrect IOL power	Postoperative refractive error different from predicted and not due to a calculation or other user error
Iris pigment epithelium loss	New or worsening iris transillumination defects or increase in pigmented cells in the anterior chamber noted after the 1-wk visit when assessed before instillation of any dilating drops Note: If there is a transillumination defect preoperatively, then a photograph should be taken, and then at each subsequent visit, a photograph should be taken and compared with the preoperative photograph via a standardized photographic method
Lens optic abnormality	Unanticipated visual outcome (e.g., acuity, contrast sensitivity, symptoms) associated with opacification, vacuoles, microvacuoles, or subsurface nanoglistenings and not due to other causes
Malpositioned IOL	Decentration, tilt, or rotation of IOL requiring reoperation
Early	If noted before 120 days postoperatively
Late	If noted at ≥ 120 days postoperatively
Damaged IOL	Crack of lens optic, breakage, or deformity of haptic, or other damage to the IOL; may include changes induced by Nd:YAG laser anterior or posterior capsulotomy
Pupil ovalization	Progressive deformation of the pupil with elongation of the pupil in the meridian of the long axis of the IOL Documentation to be made under photopic conditions NOTE: A consensus statement regarding a proposed methodology for standardizing assessment of pupil ovalization is available (Appendix 1, Masket 2017).
Pain	Graded as ≥ 4 on the standardized pain numeric rating scale of current pain intensity from 0 (no pain) to 10 (worst possible pain) Refer to the MOP for the standardized numeric pain scale (McCaffery 1989).
Peripheral anterior synechiae	Progressive closure of the anterior chamber angle due to propagation of anterior synechiae in the absence of obvious anterior uveitis
Patient-reported undesirable optical phenomena	Dysphotopsia (positive or negative or both), monocular diplopia, intolerable glare, halos, or other visual symptoms, not due to 1 of the indications listed

[REDACTED]	[REDACTED]	[REDACTED]
[REDACTED]	[name] [REDACTED]	[REDACTED]
[REDACTED]	[REDACTED]	[REDACTED]
[REDACTED]	[REDACTED]	[REDACTED]
[REDACTED]	[REDACTED]	[REDACTED]
